5.2 Secondary outcomes

A number of secondary and additional outcomes have been defined as relevant endpoints for antibiotic trials in childhood CAP by the IDSA [62].

2.1: Overall clinical outcome based on benefits and harms (DOOR/RADAR approach)

According to documentation of clinical response (normalization of all VS) and solicited AEs 1x/24h at the end of treatment (day 5) and each FUP visit.

Specific measurement: Documentation of clinical response (normalization of all VS, section 5.1) and solicited AEs (Table 2) 1x/24h at the end of treatment (day 5) and at each FUP visit.

Analysis metric: Desirability of outcome ranking (DOOR) [65].

Method of aggregation: Probability of better DOOR.

Time point: Day 3 (in-hospital visit), day 5 (end of treatment), day 7, 14, 21 (phone calls), and day 28 (close-out visit).

Rationale: The novel *response adjusted for duration of antibiotic risk* (RADAR) methodology utilizes a superiority design [65]. In RADAR, all trial participants are assigned a DOOR. The DOOR is constructed using a 2-step process: (1) categorization of all patients into an overall clinical outcome (Table 3), and (2) ranking participants in the trial using 2 rules: (2a) when ranking the outcomes of 2 patients with different overall clinical outcomes, the patient with a better overall clinical outcome receives a higher rank; and (2b) when ranking the outcomes of 2 patients with the same overall clinical outcome, the patient treated with placebo receives a higher rank. These DOOR ranks are then compared between the treatment arms with regard to the probability of a better DOOR for a randomly selected patient with placebo vs. azithromycin (i.e., Wilcoxon-Mann-Whitney statistic [66]). The DOOR/RADAR approach is helpful for RCTs to define the optimal therapeutic strategy, since considering exclusively the primary endpoint may not allow researchers to accurately balance a proven benefit with other potential harms (i.e., impaired effectiveness or side effects/AEs).

Table 2: Solicited adverse events (AEs) grading [66, 67].

Symptom	Mild (grade 1)	Moderate (grade 2)	Severe (grade 3)
Diarrhea	Looser than normal stools occurring 3-6 times/day	Looser than normal stools occurring >6 times/day	Bloody diarrhea, or diarrhea that requires medical intervention, laboratory testing, or hospitalization
Vomiting	1 episode/day	2-3 episodes/day	≥ 4 episodes/day

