Abdominal pain	Mild or intermittent and does not interfere with daily activity	Moderate or persistent and interferes with daily activity but did not need a medical visit or absenteeism from daily routine	Prevents daily activity and resulted in medical visit or absenteeism
Allergic reaction (rash and/or pruritus)	Localized rash or pruritus without rash	Diffuse rash (maculopapular or urticarial)	Generalized rash consistent with Stevens-Johnson syndrome, erythema multiforme, or toxic epidermal necrolysis; anaphylaxis; or angioedema
Oral/pharyngeal thrush or nappy rash (Candidiasis)	Mild mucocutaneous candidiasis or diaper dermatitis, with no treatment or topical treatment only	Moderate mucocutaneous candidiasis requiring oral antimicrobial treatment	Severe mucocutaneous candidiasis; requires medical intervention, intravenous treatment, or hospitalization

Table 3: Overall clinical outcome.

Outcome	Adequate clinical response*	Solicited AEs**
1	Yes: normalization of all VS	No
2	Yes: normalization of all VS	Mild (grade 1)
3	Yes: normalization of all VS	Moderate (grade 2)
4	Yes: normalization of all VS	Severe (grade 3)
5	No: no normalization of all VS without additional ED or clinic visit or hospitalization	Any grade
6	No: no normalization of all VS with additional ED or clinic visit but without hospitalization	Any grade
7	No: no normalization of all VS with hospitalization (admission, re-admission, or ongoing hospitalization)	Any grade
8	Death (any cause)	

* Adequate clinical response defined by the co-primary outcome normalization of all VS (section 5.1).

** Solicited AEs are defined in Table 3.

2.2: Time (days) to normalization of CAP-related symptoms (i.e., cough, shortness of breath, wheeze, chest pain, sore throat, nasal congestion or runny nose, headache, muscle aches or pains, nausea or vomiting, diarrhea, reduced general condition, decreased appetite, not sleeping well, reduced activity).

Specific measurement: Documentation of symptoms 1x/24h according to a validated measure for childhood respiratory infections [68, 69] by parent and the child until normalization.

Analysis metric: Time to event (days).

Method of aggregation: Hazard/median time to event.

Time point: Time point of resolution of all CAP-related symptoms.

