6.2 Methods of minimizing bias

6.2.1 Randomization

Patients will be allocated 1:1 to either azithromycin for 5 days or matching placebo for 5 days through minimization, which allows balance between treatment groups for several characteristics at all stages of the trial [78].

The following characteristics will be considered:

- 1) **Age:** 3-9 years vs. 10-17 years [7].
- 2) **Patient care status:** ambulatory vs. hospitalized.
- 3) **Duration of respiratory tract symptoms and/or fever before presentation to the ED:**
≤6 days vs. >6 days [43, 79].
- 4) **Participating center:** 13 centers.

The allocation of a participant to the IMP based on the aforementioned characteristics will be done using the electronic data capture (EDC) system secuTrial®. The first participant will be truly randomly allocated by the system; for each subsequent participant, the treatment allocation that minimizes the imbalance on the selected characteristics between groups at that time will be identified by the system. This allocation will be made with a probability of 0.8 in favor of the intervention that would minimize imbalance between treatment groups. The random element (of 0.2) ensures that allocation is not fully deterministic.

The ZüriPharm AG at the University Hospital Zurich will assemble, blind, label, and distribute the IMP for each site to guarantee all safety regulations. Each kit (IMP, oral syringe, and measuring cup) has a unique medication ID. The medication ID and the associated treatment (active drug and placebo) are linked in a medication list, which is stored in secuTrial® by the study data manager at the CTC Zurich. The medication list in secuTrial® includes medication IDs for medication that is available at each center (e.g., ZH123, LU123) and guarantees enough supply for each treatment arm. The medication list is concealed to all other parties.

Prior to allocation, the local investigators (study physician or study nurse) must enroll the participants who fulfill all inclusion/exclusion criteria via the EDC and enter the respective characteristics. The EDC will then allocate the medication ID to the patient by minimization and release the medication ID to the investigator. Patients will be allocated to the IMP at the ED (for ambulatory patients) or as closely as possible to hospital admission (for hospitalized patients) within a maximum of 6h after ED admission.

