7. STUDY POPULATION AND INFORMED CONSENT PROCEDURE

7.1 Eligibility criteria

Inclusion criteria:

Inclusion criteria for screening phase:

- **Children aged 3-17 years** (from 3rd up to 18th birthday) presenting to the ED who will be managed ambulatory or will be admitted to general ward.
- **Clinical diagnosis of CAP:**
 - 1) **Diagnosis defined as the treating physician's documented diagnosis of CAP;** AND
 - 2) **Fever $\geq 38.0^{\circ}\text{C}$** (measured by any method [i.e., ear, axillary, rectal, or forehead site] in the ED or via parent report observed in the last 24h); AND
 - 3) **Tachypnea** (RR above the age-specific reference value as defined in section 5.1, Table 1 during the assessment in ED [triage or clinical examination]).

This trial aims to produce translational results generalizable to a “real-world” setting. In ED settings, the diagnosis of CAP is generally based on clinical criteria [8, 9]. Therefore, inclusion criteria for this study will not be based on radiological or laboratory diagnostics. However, according to our experience from previous studies and feedback from participating centers, we expect $\geq 90\%$ of children to have a CXR performed as part of their diagnostic routine.

- **Written screening consent for participation in screening phase** signed by parents or legal guardians and the patient if ≥ 14 years of age.

Additional inclusion criteria for intervention phase:

- **Positive *Mp* screening test result** with the *Mp* IgM LFA (grade 2 or 3) (section 6.1).
- **Written informed consent for participation in intervention phase** signed by parents or legal guardians and the patient if ≥ 14 years of age.

Exclusion criteria:

Exclusion criteria for screening phase:

- None.

Exclusion criteria for intervention phase:

- Contraindication to azithromycin: Documented allergy to azithromycin; cardiovascular disease, including bradycardia, arrhythmias, and/or QT-interval prolongation*; myasthenia gravis.
*Co-medication with arrhythmogenic or QT-interval-prolonging drug (<https://crediblemeds.org>) is no exclusion criteria but will be discussed with the local investigators and/or TMT.
- Underlying comorbidities: Cystic fibrosis or other chronic lung disorders (excluding asthma), primary or secondary immunodeficiency, sickle-cell anemia, or severe cerebral palsy.

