11.4.3 Secondary Analyses

The secondary outcome “overall clinical outcome based on benefits and harms” will be compared between treatment groups in terms of the probability of having a more desirable outcome with placebo than with azithromycin (Wilcoxon-Mann-Whitney statistic) as a summary contrast measure, as usual with the DOOR/RADAR approach [65]. DOOR is constructed using the (1) categorization of all patients into the overall clinical outcome, and (2) ranking patients in the trial according to two rules: (2a) when ranking the outcomes of two patients with different overall clinical outcomes, the patient with a better overall clinical outcome receives a higher rank; and (2b) when ranking the outcomes of two patients with the same overall clinical outcome, the patient treated with placebo receives a higher rank. This DOOR outcome is then compared with a Wilcoxon-Mann-Whitney test with a confidence interval on the Wilcoxon-Mann-Whitney statistic that is compatible with the test. In addition, we will estimate the probability of a more desirable outcome without adjusting for antibiotic use, i.e., just comparing the overall clinical outcome between treatment groups, otherwise using the same method.

Other secondary outcomes which measure a duration will be analyzed by mixed-effects Cox proportional hazards models (with a random intercept per center) to estimate a hazard ratio. Binary secondary outcomes within 28 days will be analyzed by binary generalized linear mixed-effects models (with logit-link) to estimate OR. Repeated measurements of the secondary outcome QoL will be analyzed by a linear mixed-effects model with random intercepts for center and subject (nested within center). The serial autocorrelation of residuals within subjects will be modeled using a first order autoregressive correlation structure. Treatment, visit, and the interaction between treatment and visit will be used as explanatory terms. All effect size estimates for secondary outcomes will be reported with

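### DOOR class 7 pools an ongoing index stay with new admission, so early DOOR classes depend strongly on baseline care status, which the planned comparison ignores

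*Protocol*

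**What the plan says.** Section 7.1 admits children "presenting to the ED who will be managed ambulatory or will be admitted to general ward", so both groups enter the trial. Section 6.2.1 makes baseline care status, "ambulatory vs. hospitalized", a minimization factor.

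Table 3 in section 5.2 grades children whose vital signs (VS) have not normalized by their use of care. Class 5 is "No: no normalization of all VS without additional ED or clinic visit or hospitalization". Class 6 adds an ED or clinic visit. Class 7 is "No: no normalization of all VS with hospitalization (admission, re-admission, or ongoing hospitalization"). Classes 1 to 4 require normalized VS, so an inpatient whose VS are normal is not in class 7.

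DOOR is ranked at "Day 3 (in-hospital visit), day 5 (end of treatment), day 7, 14, 21 (phone calls), and day 28 (close-out visit"). Within a class, rule 2b applies: "when ranking the outcomes of 2 patients with the same overall clinical outcome, the patient treated with placebo receives a higher rank". Section 11.4.3 states "This DOOR outcome is then compared with a Wilcoxon-Mann-Whitney test", and in addition "we will estimate the probability of a more desirable outcome without adjusting for antibiotic use". Neither comparison has a term for care status. The same section makes covariate-adjusted analyses of secondary outcomes optional.

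**The concern.** Class 7 mixes two different things: a stay that began before randomization and has not yet ended, and an admission that happened afterwards. At days 3 and 5, when many children are still unwell, two children with the same abnormal VS and no new event sit two classes apart only because one was admitted at presentation. An ambulatory child who returns to the ED (class 6) also outranks an index inpatient on an expected course.

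DOOR is one of the named safety outcomes (section 5.4). A reader of the day 3 or day 5 table cannot tell how much of class 7 reflects events after randomization. The unstratified rank test also carries between-child variation that was known before allocation.

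**Working it through.** **Inputs from the protocol.** 99% of children normalized by day 28 under an exponential model, median 4.2 days (section 11.2); 32% hospitalized in the earlier cohort (3.5); median fever duration 2 days (5.1); 5% risk of a CAP-related change in care status over 28 days (11.2); 376 children (11.2).

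**Assumption.** q is the share of non-normalized index inpatients still in hospital on day d. The protocol gives no planning figure for length of stay, so q is varied.

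**Step 1, the plan's own figure.** Rate = −ln(0.01)/28 = 0.1645 per day. Median = ln(2)/0.1645 = 4.21 days, which matches the stated 4.2.

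**Step 2, share not normalized.** S(d) = exp(−0.1645 d): 61% at day 3, 44% at day 5, 32% at day 7, 1% at day 28.

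**Step 3, make-up of class 7.** Index stays = 0.32 × S(d) × q. For new admissions, take an upper bound: the whole 28-day 5% has already been admitted and is not normalized, about 19 of 376.

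| | q = 1 | q = 0.5 | q = 0.25 |
|---|---|---|---|
| Day 3: index stays (of 376) | 73 | 37 | 18 |
| Day 3: share of class 7 | 80% | 66% | 49% |
| Day 5: index stays (of 376) | 53 | 26 | 13 |
| Day 5: share of class 7 | 74% | 58% | 41% |

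**Step 4, when index stays are the majority.** Solve 0.32 × S(d) × q > 0.05:

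- 4.2-day median: q > 0.05/(0.32 × 0.61) = 0.26 at day 3; q > 0.05/(0.32 × 0.438) = 0.36 at day 5.
- 2-day median (fever only, so a fast bound for all VS): q > 0.05/(0.32 × 0.354) = 0.44 at day 3; q > 0.05/(0.32 × 0.177) = 0.88 at day 5.
- With 20% inpatients and the 4.2-day median, the thresholds are 0.41 and 0.57. With 50% they are 0.16 and 0.23.

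These thresholds are on the cautious side, because the 5% accrues over 28 days and includes ICU transfers of inpatients.

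**Step 5, what stratifying gains.** Simulation of 4,000 trials of 376 children: two-sided 5% Wilcoxon test, unstratified against stratified by care status, without rule 2b. Assumed harm on placebo: hazard ratio 0.7 for normalization, with adverse events in 6% on placebo and 12% on azithromycin.

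- Harm as excess admissions (12.5% against 5%): day-3 power rises from about 53% to 59%.
- Harm as longer stay (for example 95% against 60% of non-normalized inpatients still in hospital, equal admissions): day-3 power rises from about 73% to 76%.
- Days 5 and 7: gains of about 0 to 2 points.
- No treatment difference: rejection stays near 5%.

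**Step 6, recoding index stays to class 5 instead.** In the longer-stay scenario, day-3 power falls from about 73% to 43%.

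**The case against.** The strongest reply is that class 7 is defensible as it stands. It requires abnormal VS and hospitalization at the assessment, and both are states after randomization. Failure to recover with continued stay is a plausible harm of withholding azithromycin, and Table 3 names it on purpose. This stands. A reader might infer that early class 7 measures nothing that happened after randomization, and the definition does not support that.

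A reader might also infer that excess admissions on placebo go unseen. They do not. Co-primary outcome 1.2 counts changes in care status with its own margin and confidence interval, and an index stay is not a change. Within DOOR, a newly admitted child still moves from class 5 or 6 to class 7.

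It is tempting to say that a new admission ties with an index stay. That holds for the Table 3 class and for the analysis without antibiotic adjustment. In the main DOOR/RADAR ranking, rule 2b breaks every between-arm tie by arm, so a newly admitted placebo child ranks above an azithromycin child still on an index stay.

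Recoding index stays to class 5 also looks attractive. If harm appears as excess admissions, it can help: in one simulation with an added 5% rate of ED visits, day-3 power rose from about 64% to 71%. If harm appears as prolonged stay, it loses far more (step 6). That is a choice between harms, not a correction.

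Finally, section 11.4.3 permits adjusted secondary analyses, and a statistical analysis plan not at hand may add them. But the protocol names an unstratified rank test and leaves adjustment optional, so the point stands against what it fixes.

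**Conclusion.** The point holds as a minor one. By definition, DOOR class at days 3 and 5 depends strongly on care status before randomization. That index stays form most of class 7 is probable at day 3 but not established: it depends on how many non-normalized inpatients are still in hospital. The protocol itself provides for discharge before the 5-day course ends (section 6.1), and with fast recovery the majority can fail at day 5.

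Bias is the reading to resist. Minimization on care status keeps the arms similar on it, so the effect is added noise and a class that is hard to interpret. With about 1% of children not normalized at day 28, little of the problem remains there. The power figures rest on the assumed harm scenarios and apply to the comparison without rule 2b.

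**What to change.** In section 11.4.3, stratify the DOOR comparison by baseline care status: a van Elteren test, with a stratum-weighted probability of a better outcome and a matching confidence interval, both with and without rule 2b. At each time point, report class 7 split into ongoing index stay and admission or re-admission after randomization. Leave the Table 3 classes as they are; moving index stays into class 5 would hide harm that appears as prolonged hospitalization.

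The cost is a few lines of text, settled before outcomes are compared by arm. No new data are needed: care status is entered before allocation, and admissions and length of stay are already collected as outcomes. The test remains simple, and under no treatment difference its rejection rate stays near the nominal level.

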5.3 Additional outcomes

Additional outcomes are as follows:

3.1: LOS (days) in hospitalized patients after index hospitalization.

3.2: Number of medical visits (apart from the study) until day 28.

3.3: Proportion of patients (re-)treated with antibiotics for any reason until 28 days and total antibiotic exposure in days up to 28 days.

3.4: Side effects/AEs/SAEs of IMP (section 10).

3.5: Microbial and inflammatory indicators:

Microbiological indicators:

- Proportion of patients who cleared *Mp* in the URT within 28 days.
- Proportion of patients in which *Mp* became resistant to macrolides within 28 days.
- Proportion of patients with change in co-detecting pathogens in the URT at day 3 and 28.

Inflammatory indicators:

- Biomarker and cytokine profiling at day 3 and 28.

Other additional outcomes independent of study intervention:

4.1: Degree of usefulness of informational video about the study on a five-point Likert-scale.

5.4 Safety outcomes

The main outcomes regarding safety include the co-primary outcome (1.2, CAP-related change in patient care status), secondary outcomes (2.1, overall clinical outcome based on benefits and harms, and 2.5, development of *Mp*-associated extrapulmonary manifestations), and additional outcomes in section 5.3, such as unscheduled medical visits, (re-)treatment with antibiotics, and side effects/AEs/SAEs of IMP.

6. STUDY DESIGN

6.1 General study design and justification of design

This is an investigator-initiated, randomized, double-blind, placebo-controlled, multicenter, non-inferiority trial with two parallel groups. Previously healthy children aged 3-17 years presenting to the ED with clinically diagnosed CAP will be screened for *Mp* infection.

The Study flow is presented on page 29.

[figure not shown]
Pre-screening

The ED staff (triage nurse or treating physician) will inform the local investigators (study nurse, study physician, or GCP-trained ED consultant) about an eligible patient aged 3-17 years with clinical diagnosis of CAP. The local investigators will initiate contact and inform the parent (and patient), obtain a written screening consent, and perform the screening for *Mp* infection with the ***Mp* IgM LFA**.

Screening

Mp-specific PCR, IgM enzyme-linked immunosorbent assay (ELISA), and IgM ASC ELISpot assay are too time-consuming to be used as on-site screening tool, and no approved point-of-care (POC) test is available for direct detection of *Mp* [19]. Therefore, many previous RCTs randomized all CAP children to either macrolide or placebo (or beta-lactams) [32]. The evidence derived from these studies is insufficient to draw any conclusions about the efficacy of macrolides for *Mp* infection (section 3.1). Labsystems Diagnostics (Vantaa, Finland; <https://www.labsystemsdx.com/>) has launched a new POC LFA (Biocard™ *Mycoplasma pneumoniae* IgM) for the detection of *Mp*-specific IgM antibodies from a capillary blood sample, with results available within 10min (Figure 1). The *Mp* IgM LFA is an accurate POC test to diagnose *Mp* infection [73].

Figure 1. Biocard™ *Mp* IgM LFA. (A) Illustrative examples of positive, negative, and invalid test results. (B-C) Representative examples show test results for different specimens (B) and gradings (C) [74].

We evaluated the *Mp* IgM LFA as screening test against *Mp* PCR as reference test for MYTHIC using two CAP cohorts: the myCAP cohort ($n=94$ [74]) and the KIDS-STEP cohort ($n=66$ [75]). Applying the same inclusion criteria as in MYTHIC on both cohorts, a positive *Mp* IgM LFA result defined as moderate to strong blue test line (grade 2 or 3, Figure 1) was *good* at ruling in a *Mp* PCR-positive CAP patient with a positive likelihood ratio (LR+) of >10 (Table 4) [76, 77].

Table 4. Diagnostic performance of the *Mp* IgM LFA compared to *Mp* PCR as reference test.

Cohort, n	Characteristics	Reference test PCR	Screening test IgM LFA		Performance
			Positive (grade 2 or 3)	Negative (grade 0 or 1)	
myCAP study ($n=94$, published in [74]) and KIDS-STEP study ($n=31$, unpublished results) $n=125$ (total)	
 • CAP clinically diagnosed • Age 3-17 years • Inpatients or outpatients • Previous healthy children 	Positive	37 (29.6%)	6 (4.8%)	Sensitivity: 86.0% (95% CI 72.7%-93.4%) Specificity: 95.1% (95% CI 88.1%-98.1%) LR+: 17.64 (95% CI 6.73-46.22) LR-: 0.15 (95% CI 0.07-0.31) DOR: 120.25 (95% CI 31.99-452.07)
		Negative	4 (3.2%)	78 (62.4%)	

Abbreviations: CI, confidence interval; DOR, diagnostic odds ratio; LR+, positive likelihood ratio; LR-, negative likelihood ratio.

All screened and enrolled participants will provide a NPS sample (see Study flow), either performed as part of the clinical routine diagnostic work-up or exclusively for the use in this study. All collected NPS samples will be tested with an **Mp PCR** as reference test to verify the **Mp IgM LFA** test result. **Mp IgM LFA** false-positive participants will be excluded from the per protocol analyses (Table 5). All NPS samples will be frozen and stored locally (-20°C to -80°C depending on the infrastructure of the center). The stored NPS samples will be transferred to and analyzed by **Mp PCR** at University Children's Hospital Zurich. The results of the **Mp PCR** will not be available before the close-out visit on day 28. In case a **Mp PCR** (single- or multiplex) is performed for clinical reasons, and indicates a false-positive **Mp IgM LFA**, participants will be followed up until the close-out visit on day 28 (Table 5).

Enrollment

The **Mp IgM LFA** results will be available within 10min. In case of a positive **Mp IgM LFA** result, the local investigators will carefully check for eligibility, and obtain written informed consent for participation in the intervention phase of the trial (enrollment).

For enrolled children, a venous blood sample for the **Mp IgM ASC ELISpot assay** is required. This venous blood sample is often already routinely available (IV line and/or venous blood sampling is performed for clinical reasons in many CAP patients). However, to avoid exclusion of patients due to refusal to drawing a venous blood sample, this venous blood sample is not required for inclusion into the study. The results of the **Mp IgM ASC ELISpot assay** for the study will not be available before study closure.

The diagnostic approach with additional Mp PCR (as reference test) on screened patients and additional Mp IgM ASC ELISpot assay (as confirmatory test, section 3.1) on randomized patients will ensure a correct diagnosis and clear guidance on study procedures and statistical analyses according to different test results (Table 5). This diagnostic approach will be the major advantage compared to previous studies evaluating the effect of macrolides in children with Mp CAP.

Table 5. Diagnostic approach and test result constellations.

Test:	Method:	Turn-around time:	Specimen:	Expected test results with specific rates based on pilot results using the myCAP cohort [74] and KIDS-STEP cohort (n=125, Table 4):				
1. Screening test:	IgM LFA	10min	Capillary blood	- 67.2% n=84/125		+ Randomization 32.8% n=41/125		
Expected proportion (%) and number (n) based on pilot studies:								
2. Reference test:	PCR²	After study closure	NPS	-	+	-	+	
Expected proportion (%) and number (n) based on pilot studies:				92.9% n=78/84	7.1% n=6/84	9.8% n=4/41	90.2% n=37/41	
Interpretation in regard to IgM LFA:				Negative	False-negative	False-positive	Detection	
3. Confirmatory test:	IgM ASC ELISpot³	after study closure	Venous blood	NA ¹	NA ¹	-	-	+
Expected proportion (%) and number (n) based on pilot studies:						9.8% n=4/41	14.6% n=6/41	75.6% n=31/41
Final interpretation:				Negative	False-negative	False-positive	Carriage and/or persistence	Infection ³
Study procedure:				No randomization	No randomization	FUP until final visit on day 28 ²	FUP until final visit on day 28	FUP until final visit on day 28
Statistical analysis:				Diagnostic accuracy	Diagnostic accuracy	Intention-to-treat	Per protocol	Strict per protocol

¹ No venous blood sampling because not enrolled.

² A majority of children admitted with a diagnosis of CAP currently have a (multiplex) PCR from NPS for SARS-CoV-2 and other viruses as part of the routine diagnostic work-up and/or for patient cohorting (the placement of patients exposed to or infected with the same laboratory-confirmed pathogen in the same inpatient room). If a NPS is performed for clinical reasons, remaining sample will be stored locally (and transferred later in batches to the MYTHIC Biobank at University Children's Hospital Zurich) so that no more than one swab will be performed on patients on day 1. If a PCR for *Mp* (single- or multiplex) is performed for clinical reasons, false-positive tested participants with the *Mp* IgM LFA screening test will be followed also until the close-out visit on day 28.

³ The *Mp* IgM ASC ELISpot assay may not be available in all patients (refusal to draw blood) and/or peripheral blood mononuclear cell (PBMC) viability can be decreased in very few instances (pre-analytical processing) and result in poor assay performance. If venous blood is available also *Mp* IgM enzyme-linked immunosorbent assay (ELISA) will additionally performed but these results will not be used to guide study procedures and statistical analyses.

Intervention

After the patient was allocated to the IMP, the 1st dose of the IMP will be administered immediately after allocation by study nurses or care-givers (including nurses, treating physicians) with relevant trial training. Relevant doses will be determined according to the weight-banded dosing chart (section 8.2.1, Table 7, rounded to 0.25 mL according to the oral syringe supplied with the IMP). The parent will receive detailed instructions for the administration of the IMP at the ED (for ambulatory patients) or at the ward (for hospitalized patients if discharge occurs before completion of the 5-day treatment). Dose and time point of administration will be shown in the patient self-documentation in secuTrial® or study diary.

FUP

In-hospital FUP study visits will be performed at day 3 and 28, including a clinical assessment as well as NPS and capillary blood sampling. FUP phone calls will take place at day 7, 14, and 21 to ensure data collection and query additional symptoms.

Sample processing

Venous blood samples from enrolled patients will be sent directly to the MYTHIC Biobank at University Children's Hospital Zurich. NPS samples and capillary blood from screened and enrolled patients will be frozen and stored locally and transferred later in batches to the MYTHIC Biobank at University Children's Hospital Zurich.

